Study Protocol

Adherence to HIV Treatment Postpartum: The Implications of Transitions Among Women Living with HIV in South Africa

ClinicalTrials.gov #: NCT04846569

Version 5.0

November 5, 2021

IRB Federalwide Assurance Numbers:

- FWA00004460 (Brown University)
- FWA00001637 (University of Cape Town)

Study Sponsor: National Institute of Mental Health (K01MH112443)

Protocol Summary

Adherence to HIV Treatment Postpartum: The Implications of Transitions Among Women Living with HIV in South Africa

Study Aims:

Aim 1: Identify contextual, interpersonal, clinic, and individual-level factors that influence women's HIV treatment adherence during periods of key points of transition during pregnancy and postpartum, using longitudinal in-depth qualitative interviews among a cohort of pregnant women (N=25-30) following them up to 12 months postpartum.

Aim 2: Evaluate the feasibility and preliminary efficacy of a Transition Theory-based ART adherence intervention for postpartum women living with HIV, using a small scale randomized controlled trial (RCT; N=60).

Aim 3: Assess participants' experiences of the intervention, perceived usefulness, and identify ways to refine the intervention for future evaluation, using in-depth individual interviews will be conducted with all participants in the intervention condition after follow-up assessments have been completed.

Sample size for RCT: 62 participants consented; 43 randomized

Study population: Adult (≥ 18 years), HIV-positive, pregnant (23-34 weeks) women attending antenatal services at the study site, prescribed ARVs

Participating site: Gugulethu Midwife Obstetric Unit, Cape Town, South Africa

Study design: Small-scale two-arm randomized control trial, assessing feasibility and preliminary efficacy.

Study timeline for RCT: April 2021-December 2022

Principal Investigator:

[name]
Assistant Professor of Behavioral and Social Sciences
International Health Institute
Brown University School of Public Health
[name]
[name]
[name]
[contact]

Co-Investigators/K01 Mentors:

[name], PhD

Professor of Epidemiology and Biostatistics
School of Public Health and Family Medicine
University of Cape Town
Cape Town, South Africa
[name]
[contact]

[name]
Professor, Behavioral and Social Sciences
Brown University School of Public Health
[name]
[name]
[contact]
[contact]

[name]
Associate Professor, Epidemiology

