
Introduction

It is a critical time in the South African HIV epidemic to increase HIV treatment adherence among postpartum mothers. During pregnancy and postpartum, women living with HIV are eight times more likely to die than women who are HIV negative.¹ Prevention of mother-to-child transmission (PMTCT) efforts have reduced rates of vertical transmission to 2.7% in South Africa (ZA),² however, optimal postpartum adherence to HIV treatment, a key

component of PMTCT, remains difficult.^{3,4} There are significant consequences of non-adherence postpartum including viral rebound,⁵⁻⁷ which increases infectiousness to sex partners⁸ and infants while breast-feeding,⁹ and an increased chance of drug resistance,¹⁰⁻¹⁴ which is particularly concerning in resource-limited settings where additional lines of ART may be limited.¹⁵ Women who are non-adherent are also at risk for AIDS-related complications, including tuberculosis,¹⁶ candidiasis,¹⁷ and cytomegalovirus,¹⁸ which can create high-risk pregnancies and jeopardize maternal and infant health.

Option B+ policies, which provide antiretroviral therapy (ART) to all HIV positive pregnant women for life, regardless of CD4 T cell count, have been adopted in many countries as a way to simplify health services and increase access and uptake.^{19,20} There is major concern, however, about suboptimal engagement in care postpartum after mothers transfer from antenatal clinics to regular adult HIV care and the ability for women to adjust to lifelong treatment.²¹⁻²⁵ In Cape Town, ZA, 49% of women living with HIV have disengaged from care by six months postpartum²⁶ and a meta-analysis³ of 51 studies found that only 53% of the women had optimal adherence postpartum. Additionally, it is hard to determine with precision when drop-offs in ART adherence occur due to the wide range of time points (3 days to 12 months) used to denote “postpartum” adherence in the literature.²⁷⁻³³ In order to fully capitalize on the potential that Option B+ has for simplifying HIV treatment, it is necessary to identify when and why women become non-adherent to ART and how influential factors may change as HIV positive mothers transition from pregnancy to postpartum.

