Our team has extensive experience in utilizing data from routinely collected electronic medical records in this setting, including for ART and PMTCT outcome assessment.^{60,61} Data will be requested from the Western Cape Provincial Data Centre, and we will use participants' provincial folder number (requested as part of tracing information) to facilitate an accurate electronic data request. Permission to review electronic clinical records of participants will be included in informed consent documents. Following standard procedures, we will request approval from the Provincial Department of Health to access electronic medical records. Established procedures are in place to ensure patient confidentiality. The project manager will link these data to participants' unique participant identifiers.

For the primary outcomes obtained from routine medical records (engagement in care and HIV viral suppression), we will use the following definitions:

- Engagement in care will be classified as any evidence of engagement in routine HIV services, including evidence of: HIV visit attendance; ART collection at a pharmacy; laboratory testing of HIV viral load or CD4 cell count
- HIV viral suppression will be classified as a viral load <200 copies/mL

For the primary outcome, we will use a window of up to 3 months around the 6-month postpartum study visit. In cases where there is evidence of multiple HIV viral load results in this window, we will use the result closest to the 6-month postpartum study visit for the primary outcome. For women who are lost to follow-up, we will use the median time of visits attended among those who are retained at study measurement visits to assess engagement in care and HIV viral suppression. As the primary outcome data will come from routine medical records, all women will have outcome data regardless of retention at study measurement visits.

Routinely collected clinical data will be linked with the written permission of (a) the participant (via informed consent), (b) the research oversight body of the Provincial Government of the Western Cape including the Provincial Data Centre, and (c) the HREC. Established procedures are in place to ensure patient confidentiality.

Aim 3 Qualitative Component

In-depth interviews will be conducted with participants randomized to the intervention condition (n=up to 30) after the completion of follow-ups in order to assess participants' experiences of the

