Sample size considerations: pilot study

The overall goal of this pilot study is to determine feasibility and potential efficacy to support future larger, fully-powered tests of the intervention's efficacy. We fully acknowledge the exploratory nature of this pilot. With a sample size of 60, between two groups, 2 follow-up measurements, controlling for self-reported baseline adherence, $p=0.05$, we will have 29% power of finding a small effect (Cohen's $d=0.30$), 65% power of finding a moderate effect ($d=0.50$), and 98% power of finding a large effect ($d=0.80$). This study will be underpowered to find significant small and moderate effects however, we will be able to calculate an effect size and the direction of its impact to support a larger scale test of the intervention.

The facility that is participating in this study, the Gugulethu MOU, sees approximately 4800 pregnant and postpartum women annually, with an antenatal HIV prevalence of 28%. Thus, we do not anticipate difficulty recruiting this sample within the allotted timeframe.

Sample size considerations: In-depth Interviews (Aim 3)

We propose to interview all of the women randomized to the intervention condition ($n=$ up to 30). Based on our follow-up rates for the longitudinal qualitative cohort (HREC 344/2017), we anticipate at least an 80% retention rate at 6 months postpartum, which equates to an anticipated 24 participants completing in-depth interviews. Based on our previous experiences working with this population, we feel that 24 participants will be enough to reach saturation on key themes related to acceptability of the intervention.

Data management

The study includes data from four sources: (1) interviewer-administered questionnaires; (2) routine electronic medical records; (3) dried blood spots; and (4) IDI with participants randomized to the intervention condition. The collection of data will be conducted by (1) a fieldworker; (2) the project manager; (3) lab-based researcher; and (4) a qualitative interviewer, respectively. Procedures for data collection (regardless of source) will be outlined in SOPs. We have a bank of well-developed SOPs that our group has developed for previous studies. All data management will take place at UCT following procedures established by our group for multiple previous studies.

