Quantitative data will be captured into a custom designed Microsoft Access database. The database will be password-protected following standard password safety procedures, and will be maintained in a firewall-protected UCT server with daily backups. The database will be designed and maintained by the project manager. The study coordinator will direct queries and data

quality assurance (QA)/quality control (QC) activities, and supervise data entry, with oversight from the project manager. Data QA will be in the form of robust database structure and platform, and 'front-end' data checks including real-time database queries. QC will be through data checking scripts to identify out-of-range values, logic violations and missing observations. Queries will be resolved based on reference to the completed questionnaires in question; all data queries and responses will be logged, and edits will be implemented through separate program files.

Qualitative data from IDI will be transcribed verbatim and translated into English. Translations will use unique participant identifiers, not participant names. All electronic files will be encrypted and password protected.

Data analysis

Quantitative data will be exported to Stata Version 14.0 (Stata Corporation, College Station, Texas) for analysis. We will analyze all primary and secondary outcomes preliminarily using simple means and standard deviations and point-biserial correlations to estimate effect sizes where appropriate. For outcomes that are indicative of a possible difference by condition, we will utilize more advanced analytic techniques, i.e generalized estimating equations (GEE), as follows:

To compare the impact of intervention condition on self-reported ART adherence, engagement in ART services and HIV viral suppression, we will utilize a series of generalized estimating equations (GEE) using Poisson distributions where appropriate. Outcome analyses will control for baseline self-reported adherence and any baseline differences on demographic variables. Intervention condition, time of assessment, and condition*time interaction will be entered as model effects. We will use GEEs to predict key psychosocial outcomes (adherence self-efficacy) by intervention condition. If there is evidence of an intervention effect we will explore factors that may modify intervention effects, we will compare intervention effects within subgroups of women based on key demographic clinical and psychosocial characteristics.

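### Up to about one in five women may lack the 6-month self-reported adherence score, and the planned attenders-only analysis can bias the arm difference if loss is tied to leaving care

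*Combined protocol and SAP*

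**What the plan says.** - **Outcome.** Section 2 lists self-reported adherence at 6 months postpartum (three items, rescaled to 0-100) among the primary outcomes. The Section 3 design text treats it as the single primary outcome.
- **Source.** Section 7, Quantitative measures: a blinded interviewer administers the questionnaires at study measurement visits. A missed visit leaves no score.
- **Expected loss.** Section 9, sample size for the in-depth interviews: "we anticipate at least an 80% retention rate at 6 months postpartum, which equates to an anticipated 24 participants completing in-depth interviews".
- **Completeness.** Section 7, Linkage of routinely collected clinical data: "all women will have outcome data regardless of retention at study measurement visits". The reason given there is that the data come from medical records, and the paragraph defines only engagement in care and viral suppression.
- **Analysis.** Section 9, Data analysis: "We will analyze all primary and secondary outcomes preliminarily using simple means and standard deviations and point-biserial correlations". Outcomes that hint at a difference then go to a GEE with condition, time and their interaction, controlling for baseline self-reported adherence and demographic variables that differ at baseline. No analysis set, imputation, weighting, missingness assumption or sensitivity analysis is stated for the self-report.
- **Background.** The Introduction cites a Cape Town figure: "49% of women living with HIV have disengaged from care by six months" postpartum.

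**The concern.** A simple mean or point-biserial correlation uses only women who attended the visit. It estimates the effect among all randomised women only if attendance is unrelated to adherence. In this population one event, leaving HIV care, could plausibly cause both a missed study visit and poor adherence.

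The intervention is meant to keep women linked to care. If it works, it changes who is seen at 6 months, and part of its benefit can disappear from a comparison of attenders. This can happen even when attendance depends on engagement in the same way in both arms.

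Section 9 says the pilot is to supply an effect size and its direction for a larger trial, so a distorted estimate would carry forward. The GEE is a limited safeguard. Its adherence covariate is measured in pregnancy, before any postpartum disengagement, and it runs only if the first-stage result already suggests a difference.

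**Working it through.** **1. The plan's own retention figure.** 30 × 0.80 = 24, as stated. Applying the same 80% to both arms (an assumption, since the figure sizes interviews in one arm):
- planned sample: 60 × 0.80 = 48 scores, 12 missing;
- number randomised ("62 participants consented; 43 randomized"): 43 × 0.80 = 34.4 scores, about 9 missing and about 17 observed per arm.

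**2. When bias arises.** Let m be the proportion lost in an arm and D the mean gap between retained and lost women. The attenders-only difference minus the true difference is m_I·D_I − m_C·D_C.
- Loss 20% and 20%, gap 20 and 20: 4 − 4 = 0.
- Loss 10% (intervention) and 30% (control), gap 20 in both: 2 − 6 = −4.
- Loss 30% and 10%, gap 20 in both: 6 − 2 = +4.

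The bias can therefore be zero or of either sign. The documents give neither m by arm nor D.

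**3. Engagement model.** From the documents: 80% overall retention, and 49% disengaged by six months (a background figure, used here as 51% engaged in the control arm). Assumed: mean score 90 if engaged and 55 if not; engagement in each arm (p); attendance a_E if engaged and a_D if not, the same in both arms, with a_D set so that overall retention is 80%.

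True arm mean = 90p + 55(1 − p).

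Observed arm mean = [p·a_E·90 + (1 − p)·a_D·55] / [p·a_E + (1 − p)·a_D].

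Example, 51% v 70% engaged, a_E = 1.0: average engagement is 0.605, so a_D = (0.80 − 0.605)/0.395 = 0.494. True means are 72.85 and 79.50 (difference 6.65). Observed means are 78.74 and 83.89 (difference 5.15). Bias is −1.50.

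Bias in points at 80% retention (percentage attenuation):

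| a_E | 51% v 70% (true 6.65) | 51% v 80% (true 10.15) | 60% v 75% (true 5.25) |
|---|---|---|---|
| 0.80 | 0 | 0 | 0 |
| 0.85 | −0.26 (4%) | −0.64 (6%) | −0.39 (7%) |
| 0.90 | −0.60 (9%) | −1.42 (14%) | −0.87 (17%) |
| 0.95 | −1.01 (15%) | −2.34 (23%) | −1.44 (27%) |
| 1.00 | −1.50 (23%) | −3.41 (34%) | −2.08 (40%) |

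In the first scenario with a_E of 0.95 to 1.0, the arm means are overstated by 3.3 to 5.9 points. With the same inputs, attenuation falls to 8-14% at 85% retention and 3-8% at 90%.

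**4. What the GEE recovers.** A large simulation used normal scores, correlation 0.5 between visits (assumed) and about 20% loss at 6 months. Results are in SD units, given as simple difference / independence GEE with baseline adjustment.

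| What drives loss | True effect | Estimates |
|---|---|---|
| Chance, or baseline adherence alike in both arms | 0.50 | 0.50 / 0.50 |
| 6-month adherence, same mechanism in both arms | 0.50 | 0.45 / 0.46 |
| 6-month adherence, control arm only | 0.50 | 0.27 / 0.32 |
| 6-month adherence, control arm only | 0 | −0.23 / −0.17 |

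Baseline adjustment removes little of the bias when loss follows postpartum adherence.

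**5. Bias against noise.** With 17.2 observed women per arm and no variation within engaged or disengaged groups, SE = 35·√[(q_C(1 − q_C) + q_I(1 − q_I))/17.2], where q is the engaged share of attenders. For 51% v 80% and a_E = 1.0, q is 0.712 and 0.905, so SE = 4.6 against a bias of 3.4. For 51% v 70%, SE is 5.1 to 5.3 against 1.0 to 1.5.

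**6. Does the alternative help?** In a simulation of 43 women with 80% retention and the 90/55 scores, attenders-only bias was about 0 to −3.4 points. Arm-specific imputation from record-based engagement and the 3-month score had bias of about 0. Its root mean squared error ranged from about 10% lower to 7% higher.

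**The case against.** A reader might infer three stronger things, and the documents support none of them.

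- **That one in five women will have no score.** The text says at least 80% retention. It is a forecast from the earlier qualitative cohort, used to size interviews. Twenty per cent is therefore a ceiling on the anticipated loss.
- **That the GEE ignores adherence.** It conditions on baseline adherence and models both follow-up visits. It is unbiased in the case where loss follows baseline adherence alike in both arms. That it is unweighted is an inference from the plan's silence.
- **That the planned estimate is biased.** Size and sign depend on quantities the documents do not give, and some reasonable inputs give zero. The 90/55 scores, the engagement contrasts and the attendance rates are all assumed. The 49% is a literature figure, not a planning value for a control arm that also receives a community health worker session.

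There are also mitigating facts. Leaving HIV care is not the same as missing a study visit: study visits are separate from routine care, compensated, and backed by calls, alternate contacts and home tracing (Sections 7, 8 and 10). Retention and assessment completion will be reported. The primary hypothesis is feasibility, and the plan admits that it is exploratory and underpowered. In every engagement scenario tried, the bias is below one standard error.

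All of this limits the size of the point. It does not fill the gap: tracing reduces loss and completion rates describe it, but neither corrects an estimate. The plan also leaves unused the record-based information it already holds on women who miss the visit.

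**Conclusion.** The point holds as a possible bias with a cheap remedy. Up to about 20% of 6-month adherence scores may be missing, the completeness statement does not cover them, and the stated analyses either compare attenders only or adjust only for baseline adherence and demographic imbalances.

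If women who disengage both miss visits and adhere less, the arm difference can shrink by 0 to 3.4 points on the 0-100 scale at 80% retention, less with better retention, and mean adherence can be overstated. These figures rest on the assumed scores, engagement and attendance rates. If loss differs by arm for other reasons, the bias could go either way. The effect is small beside the sampling error of a 43-woman trial, but sampling error shows in a confidence interval and this bias would not.

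**What to change.** In Section 9, Data analysis:

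1. State that all randomised women are analysed by assigned arm.
2. For the 6-month adherence score, use multiple imputation with a short variable list: arm, enrolment score, 3-month score and record-based engagement in care. Section 7 already sets a reference date for classifying engagement in women lost to follow-up.
3. Add viral load only if it is available for most women whose score is missing. A woman out of care may have no routine result, and the dried blood spot is scheduled with the 6-month follow-up.
4. State the assumption: given these variables, loss is unrelated to 6-month adherence. Imputation does not remove bias from loss that depends on adherence beyond them.
5. Report the attenders-only estimate alongside as a sensitivity analysis, with the number of scores observed in each arm.
6. Confine the Section 7 completeness sentence to the record-based outcomes.

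Cost: a few lines of analysis-plan wording and a little more analysis, with no new data collection. The downside is some instability of imputation with 43 women, which is why the variable list should stay short.

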2. STUDY AIM & OBJECTIVES

Study aim

The objective of this study is to identify how influential factors change during key moments of transition during pregnancy and postpartum and to construct an intervention that effectively addresses these moments of transition to bolster ART adherence for mothers living with HIV.

Study approach

This study includes two phases:

1. A longitudinal qualitative cohort to identify and characterize factors that influence women's adherence behaviors as well as perceptions and motivations for continued treatment and engagement in care and examine participants' preferences of adherence intervention structure and delivery, in order to shape the design components of the bio-behavioral intervention.
2. Conduct an open pilot and small scale RCT of the intervention to determine feasibility, and preliminary efficacy of the intervention to improve ART adherence among pregnant and postpartum women living with HIV and in-depth interviews with intervention participants to determine acceptability and to identify ways to refine the intervention for future evaluation.

Note that Phase 1 received ethical approval from UCT HREC previously (HREC: 344/2017). This protocol focuses on Phase 2 (Aims 2 & 3).

For Phase 2, the key outcomes are:

Primary Outcomes

1. Feasibility: Feasibility will be assessed through the number of counseling sessions completed.
2. Preliminary efficacy - ART Adherence: Preliminary efficacy will be assessed as the correlation between study arm and self-reported HIV adherence on the 3 item Wilson ART adherence scale (self-report, 3 item scale recoded as 0-100, 100 indicating perfect adherence in the past month) at 6 months postpartum.
3. Preliminary efficacy- Retention in HIV services: Preliminary efficacy will be assessed as the correlation between study arm and retention in HIV services at 6 months postpartum. Retention in HIV services is measured by clinic records. Retention at 6 months postpartum is measured as attended HIV clinic appointment in the past 3 months.
4. Preliminary efficacy-viral suppression: Preliminary efficacy will be assessed as the correlation between study arm and viral suppression at 6 months postpartum. Viral suppression will be measured by clinic records, with viral suppression defined as HIV viral load less than 200 copies/mL.

Secondary Outcomes

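### The baseline-adjusted GEE is run only for outcomes whose crude result already looks different by arm, so the adjusted estimates it produces are too large on average whenever a true effect exists

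*Combined protocol and SAP*

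**What the plan says.** Section 9, Data analysis, sets out two stages. The first covers everything: "We will analyze all primary and secondary outcomes preliminarily using simple means and standard deviations and point-biserial correlations to estimate effect sizes where appropriate". The second is conditional: "For outcomes that are indicative of a possible difference by condition, we will utilize more advanced analytic techniques". That sentence names GEE and ends in a colon, and the model description follows it.

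The description covers self-reported adherence, engagement in ART services and viral suppression. It includes the adjustment, "Outcome analyses will control for baseline self-reported adherence and any baseline differences on demographic variables", and the model terms, "Intervention condition, time of assessment, and condition*time interaction will be entered as model effects". Adherence self-efficacy is then added: "We will use GEEs to predict key psychosocial outcomes (adherence self-efficacy) by intervention condition". Nothing defines what makes an outcome indicative of a difference: no p-value, no size of correlation and no other rule. The p=0.05 earlier in section 9 belongs to the power statement.

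Section 2 defines the three preliminary-efficacy outcomes as crude correlations at 6 months; for retention, "Preliminary efficacy will be assessed as the correlation between study arm and retention in HIV services at 6 months postpartum". The sample size text in section 9 gives the intended use: "we will be able to calculate an effect size and the direction of its impact to support a larger scale test of the intervention".

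**The concern.** The gate and the adjusted model use the same women's data. An outcome reaches the adjusted model because its crude arm difference happened to be large enough, and the adjusted difference shares most of its sampling error with the crude one. The adjusted estimates that get reported are therefore a favourable selection. An outcome with a modest true effect and an unlucky sample gets no adjusted estimate at all.

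This matters because the pilot is meant to inform a larger trial. A planner who takes an adjusted estimate at face value will, on average, plan for too large an effect when the truth is small or moderate. Those are the effect sizes for which the protocol already says the pilot is underpowered. With no cut-off written down, nobody can later tell how strong the selection was.

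**Working it through.** **Inputs from the protocol.** 43 women randomized (Protocol Summary); 1:1 allocation (section 7, Randomization), taken here as 22 and 21; true standardised differences of 0.30, 0.50 and 0.80, which are the effect sizes used in section 9.

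**Assumptions, because the plan gives no figure.** Gates at |r| ≥ 0.1 and |r| ≥ 0.2 on the crude point-biserial correlation, in either direction; baseline-outcome correlation ρ of 0.3, 0.5 or 0.7; complete follow-up; single-visit ANCOVA standing in for the GEE.

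**Step 1: the gates on the d scale.** d = r/√(1−r²) × √[(N−2)N/(n₁n₀)], and √(41×43/462) = 1.953. So |r| ≥ 0.1 means an observed |d| of at least 0.1005 × 1.953 = 0.196, and |r| ≥ 0.2 means at least 0.2041 × 1.953 = 0.399. The standard error of the crude difference is √(1/22 + 1/21) = 0.305, so the gates lie within about 0.6 and 1.3 standard errors of zero.

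**Step 2: how selection passes to the adjusted estimate.** Write D for the crude difference and A for the adjusted one. Then Var(A) ≈ (1−ρ²)Var(D) and Cov(A, D) = Var(A), so

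E[A | pass] ≈ δ + (1−ρ²) × (E[D | pass] − δ).

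Worked case, δ = 0.30 and |r| ≥ 0.1. The limits in standard errors are (0.196 − 0.30)/0.305 = −0.34 and (−0.196 − 0.30)/0.305 = −1.63. The pass probability is 0.633 + 0.052 = 0.685. E[D | pass] = 0.30 + 0.305 × (0.376 − 0.106)/0.685 = 0.42. Then E[A | pass] is 0.30 + 0.91 × 0.12 = 0.41 at ρ = 0.3, 0.30 + 0.75 × 0.12 = 0.39 at ρ = 0.5, and 0.30 + 0.51 × 0.12 = 0.36 at ρ = 0.7.

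**Step 3: simulation.** 100,000 trials per setting, gate on crude |r|, then the ANCOVA-adjusted difference. Ranges are over ρ = 0.3 to 0.7.

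| True d | No gate | Gate 0.1: pass rate | Gate 0.1: mean adjusted | Gate 0.2: pass rate | Gate 0.2: mean adjusted |
|---|---|---|---|---|---|
| 0.30 | 0.30 | about 0.69 | 0.36–0.41 | 0.39 | 0.44–0.55 |
| 0.50 | 0.50 | 0.85 | 0.54–0.57 | about 0.63 | 0.59–0.66 |
| 0.80 | 0.80 | 0.98 | 0.81–0.82 | about 0.91 | 0.83–0.85 |

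The formula in step 2 agrees with every cell to within 0.01. A two-visit GEE with condition, time, their interaction and baseline, reading the 6-month contrast, gives the same ranges. A stricter gate inflates more: at p<0.05, a true 0.30 becomes 0.63 at ρ = 0.5.

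**Step 4: no true effect (ρ = 0.5).** The signed mean stays at zero. The mean absolute adjusted estimate rises from 0.21 with no gate to 0.29 and 0.40. Among outcomes that pass the 0.1 gate, the adjusted test rejects in about 9%, against 5% ungated. Per outcome overall, the rejection rate is not raised, because a gate can only remove tests: 0.52 pass × about 0.09 ≈ 5%.

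**Step 5: a binary example.** The Introduction reports 49% disengaged by six months, so 51% retained in control; 66% in the intervention arm is assumed. The adjusted risk difference averages 0.15 with no gate, 0.19–0.20 among outcomes passing |r| ≥ 0.1, and 0.24–0.27 among those passing |r| ≥ 0.2.

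**Step 6: what a failing outcome loses.** Simulated ratio of the crude to the adjusted standard error, expressed as the excess:

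| ρ | Continuous outcome | Binary outcome |
|---|---|---|
| 0.3 | 4% | 1–2% |
| 0.5 | 14% | 7–8% |
| 0.7 | 38% | 17–18% |

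The continuous figures follow 1/√(1−ρ²) = 1.05, 1.15 and 1.40, less a small cost for estimating the slope. For the binary outcome, ρ is the correlation on the latent scale.

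**The case against.** The strongest reply is that the plan's effect size is the crude correlation. Section 2 defines preliminary efficacy that way, and section 9 says correlations are how effect sizes will be estimated, for all outcomes. That is the most natural reading, and it stands. A reader might infer that the pilot's headline effect sizes are biased by the gate. The documents do not support this, because the correlations are ungated. What remains is that they leave chance imbalance in baseline adherence uncorrected, and that any adjusted estimate reported beside them is selected.

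It could also be said that the GEE sentences are unconditional in their own wording. But they are introduced by the colon of the gating sentence, which would otherwise have no function.

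Three further inferences should be resisted:

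- **More false positives.** The gate does not raise the error rate per outcome (step 4). Only the rate among outcomes that pass goes up.
- **Wrong power figures.** Power is stated for an analysis "between two groups, 2 follow-up measurements, controlling for self-reported baseline adherence", which a gated outcome may never receive. Even so, the stated 29%, 65% and 98% are plausible. A plain two-sample t comparison at 30 per arm gives 21%, 48% and 86%. A variance factor of about 0.63 to 0.67 brings all three within 2 points of the stated values, and the protocol gives no correlation by which to check it.
- **Bias from choosing demographics by observed imbalance.** Simulation of that choice showed no bias, so it is not part of this point.

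The pilot declares itself exploratory, and feasibility is its primary hypothesis. That limits the consequence but does not remove the selection.

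**Conclusion.** The concern holds in a limited form. The adjusted GEE is gated on the crude result with no stated threshold, and estimates that pass are too large on average when a true effect exists. At 43 women, the excess for a true 0.30 is about 0.06 to 0.11 under the lenient gate and 0.14 to 0.25 under the stricter one. For a true 0.80 it is at most about 0.05. These sizes depend on assumed gates and correlations and on complete follow-up. The direction does not depend on which of these gates applies.

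The bias is conditional on passing. It does not touch the crude correlations, and the harm is limited to planning the next trial. Outcomes that fail the gate lose precision. That loss is modest for the binary outcomes, and it is material for a continuous outcome only if baseline adherence predicts it well. The plan should be changed because the remedy is nearly free.

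**What to change.** In section 9, Data analysis, delete the condition that restricts GEE to outcomes showing a possible difference. State instead that the same model, adjusted for baseline self-reported adherence, will be fitted to self-reported adherence, retention, viral suppression and adherence self-efficacy whatever the crude result. Report each 6-month contrast with a 95% CI beside the correlation defined in section 2. For any outcome measured only at 6 months, omit the time and condition-by-time terms, which cannot be estimated there.

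The cost is a change of wording and at most four model fits. No new data are needed.
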